5.4.4. Safety Period

The overall safety period is defined as beginning at the first dose of study medication rFVIII Fc. For patients who are subsequently enrolled, the safety period ends on the date of the Final Safety Follow-up Visit (by telephone or in person), 7 to 14 days after the last dose of rFVIII Fc. For patients who fail screening, this period ends on the date that this is confirmed.

The safety period on a specific treatment regimen is as described in Section 5.2 except that the end of the patient's last treatment regimen is the end of their safety period.

5.4.5. Pharmacokinetic Period

There is no defined PK period in this study.

5.4.6. Follow-up Period

The follow-up period is defined as the period 7 to 14 days after the last dose of rFVIII Fc.

5.4.7. Inhibitor Period

For patients who develop inhibitors, safety and efficacy data analysis will be dichotomized into periods before and after this event. The date of the inhibitor, that is, the date of the first sample with a positive test result (subsequently confirmed, see Section 5.1.2.4) will be leveraged for this purpose. The start and end of the inhibitor period are the start and end the relevant period, as defined in Sections 5.4.2 and Section 5.4.4.

5.4.8. ITI Period

The ITI period is defined as the time from when a patient in the ITI sub-study begins this treatment regimen until they complete or withdraw from the study. The start of this period is the date and time of the first dose of the ITI regimen.

5.5. Electronic Patient Diary (EPD) Data

Patient recorded diary data was within this project, previously queried via a defined process which required confirmation with the patient of all changes. Taking into consideration audit findings and industry standards to control changes to patient reported data, the query process was updated to only allow changes defined as not requiring patient confirmation. No changes which were not allowable under this new process were made to the EPD data. Although consolidation of records of single vials recorded within 60 minutes of each other (SVC/L60) was classified as a change not requiring patient confirmation (as agreed with MHRA in 2014), these changes are no longer being made directly into the data, but will be applied via a programmatic data convention. In addition, true duplicate records resulting from administrative issues and hence not requiring patient confirmation of the change will be deleted. The exception to this is where both injections are in the eCRF, which do not require patient confirmation, as site notes provide an alternative source and so these can be queried and processed as per the previous process.

These programming algorithms to address these two scenarios are described as follows:

1) Record consolidation:

When a dose requires more than one vial and these vials are erroneously recorded in the EPD/eCRF as separate injections, albeit within a short time window, the change to consolidate these multiple records into one record is called Single Vial Consolidation (SVC). Based on the EPD set up, the programming algorithm to identify and consolidate the records is as follows:

- Identify all injection records within 60 minutes of one another where the variables (injection date/times, lot numbers, number of vials, and vials strength in nominal IU) are not exactly the same on each record. There are four scenarios:
 - Date and time of injections are not exactly same, and lot numbers, number of vials, and vials strength in nominal IU are not the same.

- Date and time of injections are not exactly same, but lot numbers, number of vials, and vials strength in nominal IU are the same.
- Date and time of injections are exactly same, but lot numbers, number of vials, and vials strength in nominal IU are not the same.
- Date and time of injections are exactly same, but lot numbers, number of vials, and vials strength in nominal IU are the same and these duplicates occurred for reasons which cannot be attributed to administrative issues as specified below
- Consolidate injections as follows:
 - Record with earliest injection date/time retained with corresponding contextual information
 - Combine/sum values related to the dose (e.g. lot numbers, number of vials, volume injected, nominal and actual dose) into the single retained record

If injections identified with the above algorithm have distinctly different reasons (e.g., one injection is recorded as bleeding or surgery and another is recorded as prophylaxis, additional, or OTHER), then the records should NOT be consolidated. However if one reason is missing, then consolidation can be performed.

2) True duplicates removal:

When injections are identified in the EPD with exactly the same date/times, lot numbers, number of vials, and vials strength in nominal IU, these may have resulted due to administrative issues and are therefore true duplicates. There are three types of administrative issues as follows:

- Technical transmission issue
- Entry of same record into 2 different devices
- Records duplicated in EPD and eCRF which remain despite attempts to correct the data via the query process

The programming algorithm to identify and delete the duplicates is as follows:

- Identify all injections that have exactly the same date/times, reasons for injection, lot numbers, number of vials, and vials strength in nominal IU
- Remove the duplicates and keep a single record

As with SVC, if injections identified as duplicates have distinctly different reasons (e.g., one injection is recorded as bleeding or surgery and another is recorded as prophylaxis, additional, or OTHER), then these cannot be considered duplicates and removed. However if one reason is missing, then they can be considered duplicates and removed.

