#### **10.2.4.1.4. Information to be Recorded**

The incidence of bleeding in this study will be obtained from EPDs, eCRFs, and medical records. Information on dosing and bleeding episodes treated with rFVIIIFc study drug prior to the subject being issued with an EPD upon confirmation of eligibility (Section 8.3) should be recorded in the eCRF (including date and location of bleed, type of bleeding episode, dose, date of injection, and response to treatment).

Bleeding episodes will not be reported as AEs; however, the concomitant events associated with a bleeding episode should be reported as AEs as appropriate (e.g., a fracture in an elbow).

All injections administered during a study site visit must be recorded in the eCRF. An injection administered during a clinic visit must not be recorded in the EPD. Injections cannot be logged in both places. All injections performed while the subject is in the hospital for surgery must be recorded in the eCRF.

The subject's parent/caregiver must enter dosing information into the EPD *as soon as possible after an injection and within a maximum of 7 days following the injection*, to ensure data integrity, and to facilitate appropriate medical review and dosing guidance. It is recommended that parents/caregivers enter dosing information immediately after an injection.

The clinical sites and Clinical Monitors will ensure that there is consistency between the subject's medical record, IXRS, source documents, EPD, and eCRFs. During the clinic visits and monthly telephone calls with the subject's parents/caregivers, the Investigator will verify whether or not a bleeding episode has occurred and was "spontaneous" or "traumatic." The subject's parent/caregiver will also be reminded about timely EPD completion during the monthly phone call.

If, following this discussion, the Investigator judges that the classification by the subject's parents/caregivers was incorrect, the Investigator will document it in the subject's medical records with the rationale for the new classification, and the eCRF, documenting the new classification of the bleeding episode according to the Investigator and whether or not the subject's parents/caregivers agreed with this new classification. With regard to dose changes, the Investigator's classification of spontaneous or traumatic will be used (if different from the classification recorded in the EPD by the parent/caregiver). Both spontaneous and traumatic bleeding episodes will be collected.

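### SAP 5.5 adds the EPD and eCRF copies of one injection into a double dose when their recorded times differ by 1 to 60 minutes and the other fields match

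*SAP*

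**What the plan says.** SAP 5.5 sets two programming conventions for injection records.

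- **Consolidation.** Its stated purpose is a dose made up of several vials where "these vials are erroneously recorded in the EPD/eCRF as separate injections". The programmed search is broader: "Identify all injection records within 60 minutes of one another", in any of four scenarios. The second scenario is "Date and time of injections are not exactly same, but lot numbers, number of vials, and vials strength in nominal IU are the same". The action is "Combine/sum values related to the dose (e.g. lot numbers, number of vials, volume injected, nominal and actual dose) into the single retained record", keeping the earliest time.
- **Duplicate removal.** This is for copies with an administrative cause. One of the three causes named is "Records duplicated in EPD and eCRF which remain despite attempts to correct the data via the query process". The programmed test is "Identify all injections that have exactly the same date/times, reasons for injection, lot numbers, number of vials, and vials strength in nominal IU", after which one record is kept.

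If the two recorded reasons are distinctly different, "then the records should NOT be consolidated", and the pair is not treated as a duplicate either. One missing reason blocks neither step. Pairs with both records in the eCRF are handled by query.

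Protocol 10.2.4.1.4 rules out double entry: "An injection administered during a clinic visit must not be recorded in the EPD".

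**The concern.** The SAP expects some EPD/eCRF double entries to survive querying. Its removal rule has no tolerance on time, and its consolidation rule does not look at the source of a record. A surviving copy whose time differs slightly from the original fails the first rule and meets the second. It is then handled as a second vial of the same dose.

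Two secondary endpoints take the doubled value: annualized consumption (SAP 6.6.1.4 and 7.4.7) and dose per injection to resolve a bleed (SAP 7.4.8). Total dose per bleed, average weekly prophylactic dose (SAP 6.6.1.3) and dose compliance (SAP 6.6.2.2) can also be affected. Consolidation leaves one record, so the injection count looks right and does not reveal the error.

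**Working it through.** **Step 1. Apply the rules as written to two copies of one injection.** Assumed example: one 500 IU vial, 10 kg patient, 500 IU prescribed, same lot in both records, one record in the EPD and one in the eCRF.

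| Time gap | Reasons same, or one missing | Reasons distinctly different |
|---|---|---|
| 0 min | duplicate removed: 500 IU | two records of 500 IU |
| 1, 15 or 60 min | summed: 500 + 500 = 1000 IU | two records of 500 IU |
| 61 min | two records of 500 IU | two records of 500 IU |

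In the summed cells the dose is 1000 / 10 = 100 IU/kg against a true 50 IU/kg. That is 1000 / 500 = 200% of prescribed, outside the 80% to 125% compliance band of SAP 6.6.2.2.

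**Step 2. Carry it into the bleed endpoints (SAP 7.4.8).** For a bleed treated with one injection, the number of injections stays at 1. Dose per injection and total dose both go from 50 to 100 IU/kg. The per-patient figure averages over bleeds: with k bleeds of equal dose and one affected, it rises by a fraction 1/k.

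**Step 3. Carry it into annualized consumption (SAP 6.6.1.4).** Injections per year = 365.25 / dosing interval. One doubled dose a year (an assumption) adds 1 / (injections per year), taking equal doses and prophylaxis only.

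| Interval | Injections per year | Added by one pair a year |
|---|---|---|
| 3 days | 121.75 | 0.82% |
| 4 days | 91.31 | 1.10% |
| 5 days | 73.05 | 1.37% |

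A ceiling for doses at the 12-weekly interim visits: 365.25 / 84 = 4.35 visits a year. If every visit included a dose and every such dose were affected, consumption would rise by 4.35 / 121.75 = 3.6% to 4.35 / 73.05 = 6.0%. This is a bound, not an estimate.

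**Step 4. Check what is not affected.**
- An exposure day is a 24-hour period with at least one injection (SAP 5.1.2.4). The merged record counts as one injection, so exposure-day counts do not change.
- Inhibitor incidence (SAP 9.4.3) uses test results and exposure days, not dose.
- PK doses, including the Baseline IR dose, are excluded from annualized consumption (SAP 6.6).

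**The case against.** The case for leaving the rule alone has four parts.

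1. **Safeguards come first.** The protocol forbids double entry, requires sites and monitors to keep the EPD and eCRF consistent (10.2.4.1.4), and requires vial return and reconciliation (12.1.4). EPD/eCRF duplicates are queried before the algorithm runs. Interim-visit clinic dosing happens only when needed (4.2.2.1). The error requires all of this to fail, and then matching vial fields, a gap of 1 to 60 minutes and non-conflicting reasons.
2. **The exact-match rule has a rationale.** After audit findings, the sponsor stopped making diary changes that need patient confirmation. Classing single-vial consolidation as a change that needs none was agreed with the MHRA in 2014. Two entries with the same lot and strength minutes apart are also what a genuine two-vial dose looks like.
3. **The outputs are descriptive.** No hypothesis is tested, and one non-compliant dose seldom moves a patient across the 80% compliance threshold.
4. **There is some visibility.** All injections and the dose endpoints are listed (SAP 12).

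Points 1 and 3 limit the size and stand. Point 2 is a good reason not to edit diary data, but summing is itself a programmed convention, and counting a pair once can be another. Because the protocol bars logging an injection in both places, a matching cross-source pair is far more likely a copy than a split dose. On point 4, no planned listing flags merged cross-source pairs.

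A reader might go further and infer that a caregiver and a site will almost never record the same minute, so that most surviving duplicates are doubled and study-wide consumption is materially inflated. The documents do not support that. They give no double-entry rate and no distribution of time differences. Diary entries are allowed up to 7 days after the injection, so some copies may differ by more than 60 minutes and escape summing.

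**Conclusion.** The defect holds as a matter of rule logic. Under SAP 5.5 an EPD/eCRF pair for one injection is analysed at exactly twice the true dose when lot, number of vials and strength match, times differ by 1 to 60 minutes, and the reasons agree or one is missing. No later SAP section corrects it.

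How often this happens cannot be determined from the documents. On the assumption of one pair a year, the effect on that patient's annualized consumption is about 0.8% to 1.4%. The effect on a single affected one-injection bleed is a doubling. The primary endpoint is not at risk. The change is worth making because it is specific and cheap, not because a large bias has been shown.

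**What to change.** Add a cross-source step to SAP 5.5 before consolidation:

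- Identify pairs with one EPD and one eCRF record within 60 minutes, with the same lot, number of vials and strength, and reasons that do not conflict.
- In the analysis dataset only, count the dose once and retain the eCRF record. Leave the source diary data unchanged.
- Restrict summing under the second scenario to records from the same source.
- List every such pair for review before database lock, so that a genuine dose split across the two sources can be restored.

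The cost is a short SAP edit, a few lines of code and one listing, with no new data collection. The sponsor should confirm that the convention fits its agreed process for diary data. The downside is that a true split dose is undercounted unless the review restores it.

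The change does not resolve pairs more than 60 minutes apart or pairs with distinctly different reasons. Both remain as two injections, so their total IU is still counted twice. Nor does it reach copies entered on two diary devices at slightly different times, which are same-source and would still be summed.

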5.1.2.4. Study-Specific Definitions

Exposure Day

One ED is defined as a 24-hour period in which a patient receives 1 or more doses of rFVIIIIFc, with the time of the first injection of rFVIIIIFc defined as the start of the ED.

Bleeding Episode

A bleeding episode is defined as follows: A bleeding episode starts from the first sign of bleeding and ends no more than 72 hours after the last injection to treat the bleeding, within which any symptoms of bleeding at the same location, injections ≤ 72 hours apart, are considered the same bleeding episode. Any injection to treat the bleeding episode, taken >72 hours after the preceding one, will be considered the first injection to treat a new bleeding episode in the same location. Any bleeding at a different location is considered a separate bleeding episode, regardless of the time from the last injection.

Spontaneous Bleeding Episode

Bleeding episodes are classified as spontaneous if a parent/caregiver records a bleeding event when there is no known contributing factor such as a definite trauma or antecedent “strenuous” activity. The determination of “strenuous” is at the discretion of the Investigator, and the parent/caregiver/patient will be instructed on this by the Investigator.

Traumatic Bleeding Episode

Bleeding episodes are classified as traumatic if the parent/caregiver records a bleeding episode even when there is a known or believed reason for the bleeding. For example, if a patient exercises strenuously and then has a bleeding episode in the absence of any obvious injury, the bleeding episode will still be recorded as traumatic. Target joint bleeding episodes can be traumatic if a known action leads to bleeding into the joint. The Investigator considers whether events resulting in a traumatic bleeding episode qualify as AEs and reports as such.

High and Low Titer Positive Inhibitors

A positive inhibitor test result is defined as an inhibitor test result of ≥ 0.60 BU/mL that is confirmed by a second test result of ≥ 0.60 BU/mL from a separate sample, drawn at least 2 weeks after the date when the original sample was drawn. Both tests must be performed by the central laboratory using the Nijmegen-modified Bethesda assay and the date of the inhibitor is the date of the sample with the first positive test result which was subsequently confirmed.

- A positive low titer inhibitor is defined as an inhibitor test and confirmatory test, both with results of ≥ 0.60 and < 5.00 BU/mL.

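### The SAP 5.5 diary rules merge or remove injection records without comparing bleed location, so two bleeds at different sites treated within 60 minutes can be counted as one, against SAP 5.1.2.4

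*SAP*

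**What the plan says.** SAP 5.5 sets two programming rules for injection records.

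- **Rule 1, consolidation.** Its stated target is a multi-vial dose entered in pieces: "When a dose requires more than one vial and these vials are erroneously recorded in the EPD/eCRF as separate injections". The selection step is "Identify all injection records within 60 minutes of one another", with four scenarios built on "injection date/times, lot numbers, number of vials, and vials strength in nominal IU". The fourth scenario covers records identical on all of these that have no administrative explanation. For the merged record the instructions are "Record with earliest injection date/time retained with corresponding contextual information" and "Combine/sum values related to the dose".
- **Rule 2, true duplicates.** The matching step is "Identify all injections that have exactly the same date/times, reasons for injection, lot numbers, number of vials, and vials strength in nominal IU"; one record is then kept. The lead-in names three administrative causes: a transmission fault, entry on two devices, and duplication between diary and eCRF.

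The one bar in both rules is a clearly different reason for injection, illustrated by bleeding or surgery against prophylaxis, additional or other. A blank reason is no bar. For rule 1: "However if one reason is missing, then consolidation can be performed". Rule 2 has a parallel sentence.

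The episode definition in SAP 5.1.2.4 reads: "Any bleeding at a different location is considered a separate bleeding episode, regardless of the time from the last injection". Protocol 10.2.4.1.1 agrees, and Protocol 10.2.4.1.4 lists bleed location among the items the diary collects.

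**The concern.** Location decides whether two bleeds close in time are one episode or two, and neither rule in SAP 5.5 consults it. A knee bleed and an elbow bleed can carry the same reason, so the reason bar does not stop a merge, and the merged record keeps only the earlier site.

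SAP 7.4.1 derives the bleeding endpoints from these records. At stake are ABR (SAP 7.4.3), ABR by type and location (SAP 7.4.4), the spontaneous joint bleed endpoint (SAP 2.2.2), and dose per injection to resolve a bleed (SAP 7.4.8), because the pooled dose is credited to a single bleed. For episode counts the error can only go downward. None of the listings named in SAP 12 is for consolidated or removed records, so a reader of the report could not readily see it.

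**Working it through.** The plan states no figure on this point, so there is nothing to reproduce. The check applies the SAP 5.5 rules literally to pairs of test records and counts episodes by SAP 5.1.2.4 (same location within 72 hours is one episode; different location is separate).

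| Test pair | Episodes by 5.1.2.4 | After 5.5 | If locations are kept separate |
|---|---|---|---|
| Knee and elbow, 30 min apart, both spontaneous | 2 | 1 | 2 |
| Knee and elbow, 30 min apart, one spontaneous, one traumatic | 2 | 1 if both count as bleeding; 2 if they are distinct reasons | 2 |
| Knee and elbow, identical time, lot, vials, strength and reason | 2 | 1 | 2 |
| Knee and knee, 30 min apart | 1 | 1 | 1 |
| Knee and elbow, 90 min apart | 2 | 2 | 2 |
| Prophylaxis, then a bleed 30 min later | 1 | 1 | 1 |

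**Dose.** Take 250 IU per record (an assumption for illustration). In the first pair, rule 1 keeps 250 + 250 = 500 IU, all attached to the knee. The third pair could arise from one 250 IU injection entered once per site. Rule 2 would then leave 250 IU. Rule 1, scenario 4 would give 250 + 250 = 500 IU, twice what was given. The second site is lost either way.

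**Blank reason.** If the earlier record has no reason and the later one says bleed or prophylaxis, rule 1 allows the merge and keeps the earlier context, so the known reason is lost. Rule 2 does not say which record survives.

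**Effect on one child.** ABR = episodes / efficacy days × 365.25, so one lost episode lowers it by 365.25 / days. Protocol 7.3 expects participation of about 6 months to 3 years; that span stands in here for efficacy time.

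- 0.5 year: 365.25 / 182.625 = 2.0
- 1 year: 365.25 / 365.25 = 1.0
- 2 years: 365.25 / 730.5 = 0.5
- 3 years: 365.25 / 1095.75 = 0.33

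**Effect on the total bleed count.** Suppose a fraction f of N bleed treatments covers two sites, each logged as its own record, and all such pairs collapse. True bleeds are N(1 + f) and lost bleeds are Nf, so the share lost is f / (1 + f). The values of f are assumptions.

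- f = 0.02: 0.02 / 1.02 = 2.0%
- f = 0.05: 0.05 / 1.05 = 4.8%
- f = 0.10: 0.10 / 1.10 = 9.1%

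**The case against.** The strongest reply is that the rules have a narrow purpose. Rule 1 is for the vials of one dose and rule 2 for administrative duplicates. SAP 5.5 says the rules follow the diary set-up, which we cannot see; if one injection entry can hold several bleed sites, the loss may never occur. Sites also verify bleeds at visits and monthly calls (Protocol 10.2.4.1.4). This limits how often the problem can arise. It does not repair the rules: rule 1 has no field that separates vials of one dose from records for two bleeds, and the matching step in rule 2 does not test for an administrative cause.

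A reader might infer that any second bleed logged within an hour of the first is deleted. The documents do not support that. The window runs on injection time, not entry time. A second record at the same location within 72 hours belongs to the same episode, so nothing is lost. Rule 1 merges and sums; only rule 2 removes records, and it needs an exact time match. SAP 5.5 applies consolidation as a programming convention and not as an edit to the data, so the source locations remain.

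The reason bar may also protect mixed pairs. SAP 6.6.1.1 lists spontaneous and traumatic bleeds as separate reasons, while SAP 6.6 has one category for bleed treatment. The SAP leaves this open.

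Nor do the documents say that an injection with a blank reason drops out of both the bleed and the prophylaxis counts. They only allow the known reason to be lost.

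**Conclusion.** Wrong as written. The rules in SAP 5.5, followed literally, give an episode count that contradicts SAP 5.1.2.4 when two same-reason records for different locations have injection times within 60 minutes, or when one injection is entered once per site. In the second case scenario 4 of rule 1 would also double the dose. The loss of a known reason behind an earlier blank one is a smaller fault in the same text.

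An undercount is possible, not shown. The per-child effect of 0.33 to 2.0 on ABR per lost episode is arithmetic. The 2.0% to 9.1% range rests wholly on assumed frequencies and on every two-site treatment being recorded separately and merged. It should not be read as an estimate of bias in this trial.

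The affected endpoints are secondary and descriptive, with no hypothesis test. The primary inhibitor numerator comes from central laboratory results and is unaffected. The point still merits correction, because the contradiction is in the SAP text, the error has one direction for bleed counts, and it reaches a named secondary endpoint.

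**What to change.** Amend SAP 5.5 as follows.

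1. In both rules, where records carry different bleed locations, consolidate or de-duplicate the injection for dose and exposure-day counts only. Keep each location as its own bleeding episode linked to that injection.
2. Do not sum doses when identical entries describe a single injection, and state how such entries are told apart from separate vials of one dose.
3. Where one record has a blank reason or location, carry the non-missing value to the retained record.
4. State whether spontaneous and traumatic bleeds count as distinct reasons.
5. State in SAP 7.4.8 how the dose of an injection shared by two episodes is handled.
6. List all consolidated or removed records whose locations differ.

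Do not use bleed type or onset date alone as a bar to consolidation. That could leave the vials of one dose as separate injections and inflate the number of injections per bleed.

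The cost is SAP wording, some programming and one listing. No new data are needed, since location and type are already collected. The programming effort depends on the diary structure, which the documents do not show.
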